# Statistical Methods, Data Analysis and Interpretation

**Sample Size and Randomization:** There are two arms to the study. The main study is a randomized controlled trial with non-inferiority design and participants will be assigned 1:1 to either the copper T380 IUD or the LNG20 IUD for EC. The non-inferiority margin is 2.5% and we assume a pregnancy rate of 0.1% for copper IUD EC users and a 1% EC pregnancy rate for LNG IUD users. This estimate, based on our current COLIEC study (IRB# 50483) is conservative, falling within the 95% confidence interval (CI) of 0%-5.2% of the pregnancy rate of LNG20 IUD plus oral LNG for EC users. To achieve 80% power to detect a twosided 95% CI around the EC pregnancy incidence, a percent difference that does not cross the 2.5% noninferiorty margin, will require 335 participants per study arm (total of 670). We will recruit an additional 5%, 36 participants, (total of 706) to accommodate for potential early loss to follow up. Five percent is a conservative estimate based on our prior successful IUD EC studies. Even with obtaining multiple points of contact information and testing them prior to enrollment this can be a difficult population to maintain contact with. In our prior EC studies at 1 month we lost contact with 12 of 218 (5.5%) IUD users in our copper T IUD vs. oral LNG study and 8 of 176 (4.5%) in the COLIEC study. The use of the 2.5% noninferiority margin is within confidence intervals of previous literature for pregnancies among oral LNG users, which is one of the clinical standards of care (1.7%; 95% CI 0.8%-2.6%) (76) and the continued protection against future unintended pregnancy explored in aim 2 makes this clinically acceptable. In addition, women who currently present for EC and decline a copper IUD are left with a choice of oral EC, which also falls within this confidence interval. While approaching the higher limit of the oral LNG per cycle pregnancy rate from the aforementioned study, it is well below per cycle pregnancy events in some subpopulations using oral LNG, which can result in pregnancy events of 5.8% for women with higher BMIs (>30BMI) and 7.3% in women who have additional unprotected sexual intercourse(28). The LNG20 IUD is not affected by BMI and offers protection against pregnancy following future intercourse.

The maximum number of participants in the entire study is 706.

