### Outcomes

Primary Outcome: Emergency contraception failures in both arms as assessed by positive urine pregnancy tests (HCG >25 IU) 4 weeks after having the IUD inserted.

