### Data Analyses:

The primary objective will be tested by non-inferiority design to test the hypothesis that the LNG IUD is no worse than the copper IUD with a noninferiority margin of 2.5%. Using Blackwelder's approach for equivalence testing,[8] comparing those who become pregnant during the menstrual cycle in which their study IUD was inserted. Noninferiority will be established if the lower bound of a two-sided 95% CI does not cross the noninferiority bound. Analysis will be by intention to treat.

For objective #2, comparison of one-year unintended pregnancy rates from women initiating the levonorgestrel IUD vs. copper T380 IUD for EC, will be assessed by Kaplan-Meier estimates. This same approach will be utilized to construct estimates of the proportion of patients who continue with their selected IUD for 1 year (continuation

proportion). Continuous variables will be assessed by t-tests and discrete variables by Chisquare testing as appropriate.

All data will be analyzed using Stata statistical software (College Station, Texas). Standard quality control methods will be employed including use of an independent data safety monitor.

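### The primary non-inferiority rule needs one margin and one direction: Objective 1 says 1% where the rest of the plan says 2.5%, and the decision sentence names the lower bound without order of subtraction or sign

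*Combined protocol and SAP*

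**What the plan says.** **Margin.** In Purpose and Objectives, the Objective 1 hypothesis gives a non-inferiority limit of 1%. Sample Size and Randomization gives 2.5% and defends it at length: "The use of the 2.5% noninferiority margin is within confidence intervals of previous literature for pregnancies among oral LNG users". Data Analyses repeats 2.5, testing that "the LNG IUD is no worse than the copper IUD with a noninferiority margin of 2.5" per cent.

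**Direction.** The decision sentence in Data Analyses is "Noninferiority will be established if the lower bound of a two-sided 95% CI does not cross the noninferiority bound". The margin is unsigned throughout.

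**Scale.** The outcome is consistently described through the unfavourable event:

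- Outcomes: "Emergency contraception failures in both arms as assessed by positive urine pregnancy tests".
- Data Analyses: "comparing those who become pregnant during the menstrual cycle in which their study IUD was inserted".
- Sample Size and Randomization: "95% CI around the EC pregnancy incidence, a percent difference that does not cross the 2.5% noninferiorty margin".

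Objective 1 does speak of efficacy, but the measure it names is again the pregnancy test. No section says LNG minus copper or copper minus LNG, or whether the bound is +2.5 or -2.5.

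**Planning rates.** "we assume a pregnancy rate of 0.1% for copper IUD EC users and a 1% EC pregnancy rate for LNG IUD users", with 80% power, a two-sided 95% CI, 1:1 allocation and 335 per arm.

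**The concern.** A non-inferiority rule needs a margin, a scale, an order of subtraction and the bound that is tested. Here the margin has two values, and the order and sign are missing.

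For an unfavourable event, the usual test-minus-control difference is LNG minus copper. A worse LNG device moves that difference upward, so the upper bound carries the evidence. The plan names the lower one. Taken literally on that difference, the sentence does not test non-inferiority. It would ask either whether an excess beyond the margin is still unproven, or whether copper is not clearly worse than LNG.

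This is the sole decision rule for the primary objective. An analyst should not have to reconstruct it from the sample size, least of all once data are available. The margin conflict needs no interpretation: one result could meet 2.5% and miss 1%.

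**Working it through.** **1. Reproduce the plan's sample size.** Inputs from Sample Size and Randomization: LNG 1%, copper 0.1%, margin 2.5 points, one-sided alpha 0.025, power 80%. With the unpooled-variance (Blackwelder) formula:

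n = (1.96 + 0.8416)² × (0.01×0.99 + 0.001×0.999) / (0.025 − 0.009)²
= 7.849 × 0.010899 / 0.000256 = 334.2, so **335 per arm**.

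670/0.95 = 705.3, rounded up to 706. Both match the plan.

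**2. What the 335 shows about direction.** The match needs the assumed LNG excess of 0.9 points to use up part of the margin (2.5 − 0.9 = 1.6). With the excess on the other side (2.5 + 0.9 = 3.4 points) the same formula gives 75 per arm. The trial was therefore sized to test the upper bound of LNG minus copper on pregnancy.

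**3. What the 335 shows about the margin.** With a 1% limit the distance is 1.0 − 0.9 = 0.1 points:

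- n for 80% power = 7.849 × 0.010899 / 0.001² ≈ 85,545 per arm.
- At 335 per arm, SE = √(0.010899/335) = 0.00570, and power = Φ(0.001/0.00570 − 1.96) = 3.7%. Exact binomial enumeration with the Wald interval gives 15.1%.

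**4. Which conventions make the sentence correct.** Take 4/335 LNG and 0/335 copper pregnancies, with a Wald interval:

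| Difference | 95% CI (points) | Bound that tests non-inferiority |
|---|---|---|
| LNG − copper, pregnancy | 0.03 to 2.36 | upper, against +2.5 |
| copper − LNG, pregnancy | −2.36 to −0.03 | lower, against −2.5 |
| LNG − copper, non-pregnancy | −2.36 to −0.03 | lower, against −2.5 |

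The three rows are the same test. The written sentence fits the second and third. On the first it points to the wrong end.

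**5. How far a literal misreading would stray.** The plan names no interval beyond Blackwelder's approach, so the interval is an assumption. The figures are exact enumeration at 335 per arm, copper 0.1%, shown as Wald / Newcombe.

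| Rule on LNG − copper, pregnancy | Passes when LNG is truly 2.5 points worse (2.6% vs 0.1%) | Most LNG pregnancies that pass with 0 on copper |
|---|---|---|
| upper bound < +2.5 (intended) | 6.6% / 1.4% | 4 / 2 |
| lower bound < +2.5 | 99.4% / 98.8% | 16 / 15 |
| lower bound > −2.5 | over 99.99% for both | no limit |

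**6. Power of the intended rule at 1% vs 0.1%.** Normal approximation 80.1%; exact Wald 76.0%; exact Newcombe 41.9%.

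**The case against.** The strongest reply is that the plan, read as a whole, leaves little doubt about direction. The hypothesis is that LNG is no worse than copper. The sample size section requires the CI of the difference in pregnancy incidence not to cross 2.5%, without singling out a bound. The 335 works only in the intended direction. Naming the lower bound is also correct under two ordinary conventions. The source cited for Blackwelder's approach may fix the convention, which cannot be checked here. All of this stands.

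A reader might infer from step 5 that the trial would declare non-inferiority about 99% of the time for a device at the margin. The documents do not support that:

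- The rule that the lower bound be below +2.5 conflicts with the sample size section. In its extreme Wald case, 16 against 0 pregnancies, the interval runs from 2.49 to 7.06 and does cross 2.5.
- The rule that the lower bound be above −2.5 lets any LNG count pass when copper has none. That contradicts the stated hypothesis and the sizing.

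Nor is the scale absent: the plan uses pregnancies throughout. What is missing is the order and the sign.

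The reply does not reach the margin. Nothing in the plan reconciles 1% with 2.5% or explains the difference. Nor does a recoverable intention make the decision sentence complete.

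**Conclusion.** Two defects in the written primary rule stand.

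1. **Margin.** It is given as 1% in Objective 1 and 2.5% elsewhere. Only 2.5% is consistent with 335 per arm; at 1% that size has 3.7% power (normal approximation; 15.1% exact Wald).
2. **Direction.** The decision sentence names a bound without order or sign. It is valid under two equivalent conventions, neither of which is written, and wrong for LNG minus copper on the pregnancy scale that the plan uses.

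Both should be corrected before analysis because they govern the only confirmatory conclusion. Neither is a flaw in the design, and the false-pass rates near 99% describe literal misreadings, not the likely analysis. The calculations assume the plan's rates and 335 evaluable women per arm. The exact figures also depend on the interval chosen. That the Wald interval has 6.6% exact error at the margin, against a nominal 2.5%, is a separate matter and adds no weight to these two defects.

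**What to change.** - In the Objective 1 hypothesis, change 1% to 2.5%, the margin on which the trial was sized and which the plan justifies.
- In Data Analyses, replace the decision sentence with: *The difference is the LNG IUD pregnancy proportion minus the copper IUD pregnancy proportion; non-inferiority is established if the upper bound of the two-sided 95% CI is below +2.5 percentage points.*

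The cost is one figure and one sentence. Data collection does not change. The sample size stays at 335 per arm with the unpooled normal-approximation interval that reproduces it.

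The interval should also be named, as a separate decision taken with the trade-off in view. At 335 per arm the Wald interval has about 6.6% exact error at the margin and 76% exact power. Newcombe has about 1.4% error but only 42% power. Moving to Newcombe would therefore leave the trial underpowered at its present size; correcting the bound alone settles neither error control nor power.

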# **Purpose and Objectives**

In this prospective observational study, all women presenting for Emergency Contraception (EC) at Planned Parenthood Association of Utah (PPAU) clinics will be counseled using a standardized script; those interested in an IUD, who meet study qualifications and agree to participate, will be randomized to either the hormonal IUD (LNG 52mg IUD commonly known as Mirena® or Lilleta®) or the copper IUD (Paragard®). Participants will be followed for one year. If enrollment goals are not achieved due to a lack of willingness among potential participants to be randomized then we will initiate a PPC (patient preference cohort). In that case, participants who are interested in the study and eligible for participation but not willing to be randomized will be offered participation in a PPC.

This study has three specific objectives.

**Objective 1**: Determine the efficacy of the levonorgestrel IUD and copper T380 IUD for emergency contraception as assessed by urine pregnancy tests 1 month after EC use.

*Hypothesis*: The LNG IUD is non-inferior to the copper T380 IUD for EC based on a 1% non-inferiority limit.

**Objective 2**: Compare the one-year unintended pregnancy rates from women initiating the levonorgestrel IUD vs. copper T380 IUD for EC.

*Hypothesis*: At one-year the LNG IUD users will have lower pregnancy rates compared to copper IUD users.

**Objective 3:** Assess the one-year continuation, satisfaction, pain, and bleeding patterns of a LNG20 IUD to a copper T380 IUC as a method of EC and the mechanisms of continuation.

*Hypothesis*: The LNG IUD will have superior rates of continuation and non-inferior satisfaction (what about pain and bleeding patterns) compared to the copper IUD as a method of EC and the mechanisms of continuation.

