### Secondary Outcomes:

one-year unintended pregnancy rates

Assess the one-year continuation, satisfaction, pain, and bleeding patterns of a LNG20 IUD to a copper T380 IUC as a method of EC

- Pregnancy rates in the first year after presenting for EC
- Timing of IUD insertion relative to time in the menstrual cycle (pre-ovulatory, ovulatory, post-ovulatory)
- Unplanned pregnancy rates in the first year after presenting for EC
- Effect of IUD choice on vaginal bleeding assessed monthly by Pictorial Blood Assessment Chart
- Infections
- IUD continuation, expulsions, and removals through the first year after presenting for EC
- Satisfaction with EC method and contraception chosen
- Sexual satisfaction at baseline and through the first year after presenting for EC
- Frequency of unprotected intercourse since presenting for EC
- Use of contraception in the year following presentation for EC
- New diagnosis of any STI
- IUD related complications
- Abortion
- Contraception related side effects
- Use of a barrier method for prevention of sexually transmitted infections

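### Secondary outcomes get only t-tests or chi-square: nothing uses the order of ratings, and nothing yields the interval that the satisfaction hypothesis needs

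*Combined protocol and SAP*

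**What the plan says.** The Data Analyses section gives the primary comparison a non-inferiority test and uses Kaplan-Meier estimates for one-year pregnancy and continuation. Everything else falls under one sentence: "Continuous variables will be assessed by t-tests and discrete variables by Chisquare testing as appropriate". No other method is named for these outcomes.

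The Secondary Outcomes list includes "Satisfaction with EC method and contraception chosen", "Frequency of unprotected intercourse since presenting for EC" and "Effect of IUD choice on vaginal bleeding assessed monthly by Pictorial Blood Assessment Chart", as well as pain and sexual satisfaction. None is labelled continuous or discrete. The visit descriptions under Study Procedures name satisfaction as a questionnaire topic at 1, 3, 6, 9 and 12 months but give no response scale. A note there explains that full questionnaires were not submitted.

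Under Purpose and Objectives, the Objective 3 hypothesis reads: "The LNG IUD will have superior rates of continuation and non-inferior satisfaction". No margin for satisfaction is given, and pain and bleeding are left with a bracketed question instead of a hypothesis. Power is stated for the primary outcome only.

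**The concern.** A chi-square test comparing two arms on k response levels uses k − 1 degrees of freedom and treats the levels as interchangeable labels. If one device moves answers consistently up the scale, a rank test or proportional-odds model puts that shift into one degree of freedom, while chi-square spreads it over k − 1. A real overall shift is then easier to miss.

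The second issue matters more for Objective 3. Its satisfaction hypothesis is one of non-inferiority. A chi-square p-value has no direction and no confidence interval, and a non-significant result does not show that one device is no worse than the other. A directional effect measure, its interval and a margin are needed, and the plan supplies none of these for satisfaction.

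**Working it through.** **1. The plan's own figure.** The only sample size stated is for the primary outcome. Inputs from the Statistical Methods section: "we assume a pregnancy rate of 0.1% for copper IUD EC users and a 1% EC pregnancy rate for LNG IUD users"; "The non-inferiority margin is 2.5"% ; 80% power; two-sided 95% CI.

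n per arm = (1.960 + 0.842)² × [0.001 × 0.999 + 0.01 × 0.99] / (0.025 − 0.009)² = 7.85 × 0.010899 / 0.000256 ≈ 334.2, rounded up to 335. Then 670 / 0.95 = 705.3, rounded up to 706, or 353 per arm. Both figures reproduce. They fix the numbers available but say nothing about power for satisfaction.

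**2. Chi-square against an ordered test (assumption: a consistent, proportional-odds shift).** A 1-df test at two-sided 5% with 80% power has noncentrality (1.960 + 0.842)² = 7.85. Giving the same noncentrality to a chi-square on k − 1 df, power = P[χ²(k − 1, 7.85) > 95th percentile of χ²(k − 1)]:

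| Levels k | Chi-square power | Loss from 80% (points) |
|---|---|---|
| 2 | 80.0% | 0 |
| 3 | 70.9% | 9.1 |
| 4 | 64.5% | 15.5 |
| 5 | 59.5% | 20.5 |
| 7 | 52.1% | 27.9 |

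To regain 80% with 5 levels, chi-square needs noncentrality 11.9. Since 11.9 / 7.85 = 1.52, that means about 50% more women.

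**3. A worked case.** Assumed copper-arm distribution over 5 levels: 5, 7, 13, 30, 45%. Assumed common odds ratio: 1.5. The cumulative odds 0.0526, 0.1364, 0.3333 and 1.2222, each divided by 1.5, give an LNG-arm distribution of about 3.4, 4.9, 9.8, 26.7, 55.1%. The mean proportions m are 4.2, 6.0, 11.4, 28.4, 50.1%, and 1 − Σm³ = 0.850. At 335 per arm, noncentrality = 670 × 0.850 × (ln 1.5)² / 12 = 7.80. Ordered-test power is Φ(√7.80 − 1.96) = Φ(0.83), or about 80%.

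Simulation of this case (20,000 runs) gave Wilcoxon 80.0%, chi-square 59.3%, and a t-test on the level scores 74.7%. Simulated cases with 3, 4, 5 and 7 levels, tuned to 80% power at 282, 335 and 353 per arm, agreed with the table to within about 1 point. (282 is 353 less about 20% loss, an assumption.)

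**4. How far the loss moves with the assumptions (335 per arm).**

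- Large effect, odds ratio 2.0: chi-square 97.7% v Wilcoxon 99.6% with 5 levels (5/7/13/30/45%), and 93.6% v 96.8% with 3 levels (10/20/70%). The loss is about 2 to 3 points.
- Ratings scored as numbers and t-tested: 0 to 8 points below Wilcoxon at the 80% benchmark, worst for the most skewed distribution.
- Arms differing in spread, 10/15/20/25/30% v 17/13/13/20/37%: chi-square 90.8%, Wilcoxon 5.9%. The ranking reverses.

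**The case against.** A reader might infer that the plan sends satisfaction ratings to chi-square and so gives up 10 to 20 points of power. The documents do not support that. They assign no test to satisfaction by name and do not state its scale. The analysis sentence also ends with a qualifier that leaves room for judgement. A rating, pain score or count treated as numeric would go to the t-test, where the loss is small. The number of levels, distributions, effect size and proportional-odds shift used above are all assumptions.

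The trade-off is also real. Two devices could polarise users, and chi-square would then detect a difference that a rank test misses. Category proportions by arm do show direction by inspection, even though the test does not.

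Finally, power to detect a difference is not the main issue for satisfaction, because the hypothesis is non-inferiority. Replacing chi-square with Wilcoxon alone would not establish it either.

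All of this stands, and it makes the power loss conditional. It does not answer the remaining gap. The qualifier chooses between two named tests, neither of which is designed for ordered categories. If it is read more broadly, the method is left open until the answers have been seen. No margin or interval is specified for satisfaction under any reading.

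**Conclusion.** The point holds in conditional form, as a low-cost improvement to secondary outcomes. The plan names no method that uses order and does not define the satisfaction scale. If a 3- to 5-level rating is handled as discrete and tested by unordered chi-square, about 9 to 20 points of power are lost against an ordered analysis with 80% power. This assumes a consistent shift. The range is 0 for a yes/no item to about 28 points for 7 levels. The loss is about 2 to 3 points at an odds ratio of 2.0, and chi-square gains if the arms differ in spread.

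Independently of those assumptions, a chi-square test cannot support the non-inferior satisfaction hypothesis, because it yields no directional estimate with an interval to set against a margin. The primary analysis and its sample size are unaffected.

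**What to change.** In Data Analyses, replace the general sentence with text to this effect:

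*Yes/no and unordered outcomes will be compared by chi-square. Outcomes recorded on an ordered scale, such as satisfaction, will be analysed by a proportional-odds model reporting the LNG-to-copper common odds ratio with 95% CI, with the Wilcoxon rank-sum test as a check. Outcomes recorded as counts will be analysed by a count model reporting a rate ratio with 95% CI. Category proportions will be reported by arm. Non-inferiority of satisfaction will be judged from the 95% CI against a prespecified margin.*

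State the satisfaction scale and the time point for the test (Objective 3 implies one year), and set the margin before outcome data by arm are seen. For each remaining outcome, say whether it is recorded as yes/no, ordered, count or numeric; numeric outcomes can stay with the t-test.

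The cost is wording plus the work of justifying a margin. The data and visits do not change, and the models are standard in Stata, the software already named. The downside is small: a single odds ratio relies on proportional odds and is insensitive to differences in spread, which is why the category proportions should be shown beside it.
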